Study Protocol/Statistical Analysis Plan
Evaluating Technology-Based Fall Prevention Interventions
NCT03190460

9/27/2016

Objectives

The primary study objective is to explore the effectiveness of a 16-week cognitive training (CT) intervention to reduce risk and incidence of fall in community-dwelling older adults at risk for fall. Additional objectives of the study are to explore the effectiveness of a CT intervention on cognition and functional outcomes and to examine the feasibility and acceptability of the study protocol and intervention in this population.

Outcomes

Primary Outcome. At time of allocation, participants will be provided with a Monthly Fall Calendar and instructed in its use. At the end of each day participants are asked to place one of 3 letters in the box for the day: "N" for no fall; "F" for fall; and "I" for fall resulting in an injury), considered the "gold-standard" for falls assessment (See Table 1). For purposes of this study, a fall was defined as an "unintentional". For individuals who experience multiple falls in a single day, they are asked to denote the number (ex. "F-2"). Fall calendars will be collected monthly (See Table 2), and a new calendar provided to the participant during the study period. The time period for primary outcome assessment is falls over the period of 4 months. For any fall resulting in injury, we will request permission from the participant to obtain medical records for any treatment sought at time of injury.

Secondary Outcomes. Of interest as a secondary outcome in this study is reduction in risk of fall at the end of the 16-week intervention (See Tables 1 and 2). This is defined by 1) an increase in the 10M walking speed from baseline or 2) an increase in the Balance test score from baseline.⁴⁰ As secondary endpoints, we will measure cognitive outcomes (using the Cambridge Neurological Assessment Battery [CANTAB]), additional gait and postural sway measures (using body-worn inertial sensor system, the APDM Mobility Lab, Portland, OR; See Tables 1 and 2), and disability (Gill Disability Scale). We will explore if there is retention of benefit of the intervention on fall risk, gait, balance and cognitive outcomes one month following end of the intervention. Feasibility and acceptability of the study protocol and CT intervention will also be evaluated.

Table 1. Summary of Outcome Measures and Source of Measurement

Measure	Source (Instrument/Test[s])
PRIMARY OUTCOME	

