Time point	-T2	-T1	T0	T1 (4 wks)	T2 (8 wks)	T3 (12 wks)	T4 (16 wks)	T5 (20 wks)

Eligibility screening								
Phone screening	X							
In-person screening		X						
10M walk		X						
90 sec balance								
Informed consent		X						
Run-In Period		X	X					
Vision screen								
Medication review								
Home safety check			X					
Allocation			X					
Intervention								
Active Control				XXXXXXX	XXXXXXX	XXXXXXX	XXXXXXX	
Web-based Cognitive Training				XXXXXXX	XXXXXXX	XXXXXXX	XXXXXXX	
Assessments								
Baseline								
Demographics		X						
Pre-existing conditions		X						
Medications			X					
Social Support			X					
Outcome Variables								
Primary								
Falls/Injurious Falls				X	X	X	X	*
Secondary								
Fall Risk								
10M walk		X			X		X	X
90 sec balance		X			X		X	X
Cognition			X					
CANTAB			X					
Gait/Turning					X		X	X
APDM		X			X		X	X
Postural Sway			X		X		X	X
APDM			X		X		X	X
Disability			X		X		X	X
Gill Disability			X		X		X	X
Other Variables								
Short Physical Performance Battery		X			X		X	X
Timed Up and Go		X			X		X	X
Exit Interview								

Neuropsychological Test Automated Battery (CANTAB) to provide an external method of assessment to that provided by the CT intervention (See Table 1 for specific tests). Lastly, in-home gait and mobility measures are assessed. Gait, mobility and postural sway data are

collected using a body-worn *inertial sensor* system, the APDM Mobility Lab system (APDM Wearable Technologies, Portland, OR). Use of the APDM system involves "instrumenting" the participant with 6 body worn inertial sensors (2 ankle, 2 wrist, 1 waist belt, 1 upper torso) that contain tri-axial accelerometers, gyroscopes, and magnetometers. Participants are asked to wear walking shoes during the assessments. A gait belt and guarding technique⁶¹ is used by a trained investigator during all testing for safety. Data are recorded via wireless transmission from the inertial sensors to a laptop computer and processed with Mobility Lab software. For the instrumented walking assessment, participants are first asked to walk continuous laps with approximately 180-degree turns, at their comfortable (or usual) pace. They complete four 4-meter laps and two 7-meter laps (if space allows) at usual pace. Lastly, participants are asked to walk as quickly as possible, but not so quickly that they lose their balance (2 x 4 or 7-meters; see Table 1 for measures). Participants are able to take rest breaks between activities as needed.

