Following successful completion of the run-in period, participants are randomly allocated (1:2) to either a group that is the attention control (**n=20**) or to the group that receives cognitive training (CT) intervention for a total of 16 weeks (**n=40**). Participants are not to be informed that they were assigned to "attention control" or "cognitive training" conditions; rather, individuals in both groups are told that the aim of the study is to determine whether participation in "computer learning activities" reduces the risk of falls and improves functional ability. Sealed envelopes, prepared in advance, assign the participants to one of the two groups. The randomization schedule is prepared by the consulting statistician using block randomization (blocks of 6) prior to the research team's initial visit to interested parties. This approach ensures that consent is obtained prior to disclosure of group assignment and persons consent to participate in the study, regardless of the group they are assigned to. The envelope is not opened until completion of the run-in procedure. The principal investigator, co-investigators and outcome assessors are blinded to allocation until the end of the trial.

Intervention

Cognitive training, also known as "brain training", involves scheduled completion of specific tests of executive function, visuospatial orientation and perceptual speed. The CT is completed using a web-based computer interface (Cognifit, Inc.), with task difficulty tailored to the participant's abilities. We will use the Cognifit research interface as it allows tailoring of the intervention to specific tasks selected by the research team.

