Participants assigned to the attention control condition are provided with programmatic activities that are designed to control for nonspecific treatment effects (computer use, interaction with study staff). Participants will engage in an equal number of sessions (3 sessions/week for 16 weeks) watching preselected healthy aging-related video content on the computer (e.g. NIH Senior Health videos on talking with your provider, taking medications safely, and making the most of a medical visit, how to exercise safely). Participants will be asked to briefly note any information gained from each video on a personal discussion board provided to them within the content module. We track sessions completed on a weekly basis and provide reminders as needed. Discontinuation of intervention is made on participant request.

8-, 16- and 20-week Assessments

A member of the research team blinded to intervention/control group assignment conducts participant outcome assessments at the 8-, 16- and 20-week time periods (see Table 2). These assessments occur in same setting and under similar conditions to baseline testing (e.g., same shoes are to be worn). Following the 20-week assessment, an exit interview is

completed in order to gain insight into the protocol's acceptability including participant perceptions of the CT intervention. Participant interviews use a semi-structured interview protocol as a guide to explore their experiences, overall perceived benefits, challenges and attitudes towards the study protocol. All interview sessions are digitally recorded.

ANALYSIS

All planned statistical analyses will be performed using intention-to-treat. The primary time point of interest in this analysis is the 16-week post-randomization outcome assessment; however, means, standard deviations and distributions will be used to describe the outcomes of interest at baseline, midpoint of active intervention phase and 4 weeks post completion of intervention (week 20 post-randomization). A value of $p<0.05$ will be considered statistically significant. Should there be significant differences between groups on baseline demographic variables despite randomization, we will examine the relationship between the variable and the outcome using sensitivity analyses.

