The primary outcome of interest in the proposed RCT is reduction number of falls and injurious falls (See Table 1) at the end of the intervention (16 weeks). We are also interested in the retention of effect 1-month post-intervention. Number of falls and injurious falls will be determined from fall calendar data. Between group differences will be assessed using Mann Whitney U test. Of secondary interest as outcome in this study is reduction in risk of fall which is determined by an increase in the 10M walking speed from baseline and an increase in the Balance test score from baseline. Between group differences will be assessed using Student's t-test. In exploratory analyses, we will examine the change in risk of fall over time using linear mixed models for longitudinal data. As secondary endpoints, we will measure cognitive outcomes (CANTAB), functional outcomes (walking Gill Disability, inertial sensor gait and turn measures, and ISway measures; See Table 1). Outcomes will be compared between groups using either t-tests or Mann-Whitney U tests as appropriate. In exploratory analyses, we will examine the change in outcome measures over time using linear mixed models for longitudinal data.

To better understand feasibility of the study, we will estimate the proportion of older adults found eligible for inclusion who actually agree to participate in such a study. Further, we will compare the characteristics of those who are willing to participate with those who are not. We will also evaluate numbers of study who complete the study protocol and note any differences in participant characteristics in those who drop out. We will also note the numbers of older adults who express interest in the study but are not eligible. To evaluate acceptability of the study procedures and intervention, transcripts of interview sessions will be digitally recorded and transcribed verbatim for descriptive content analysis.

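### The week-16 t-test on change in 10M walking speed and Balance score leaves out the baseline value; adjusting for it would modestly raise power at 20:40, unless the baseline correlation is high or screening has narrowed the baseline range.

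*Combined protocol and SAP*

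**What the plan says.** - **Outcomes, Secondary Outcomes:** reduced fall risk at the end of the 16-week intervention means "an increase in the 10M walking speed from baseline or 2) an increase in the Balance test score from baseline".
- **Analysis:** the same outcome is restated with the two components joined by a different conjunction, followed by the test: "an increase in the Balance test score from baseline. Between group differences will be assessed using Student's t-test". On timing: "The primary time point of interest in this analysis is the 16-week post-randomization outcome assessment".
- **Analysis, longitudinal models:** "In exploratory analyses, we will examine the change in risk of fall over time using linear mixed models for longitudinal data". The model terms are not given, nor is the way baseline enters.
- **Analysis, other secondary endpoints:** "Outcomes will be compared between groups using either t-tests or Mann-Whitney U tests as appropriate".
- **Analysis, adjustment:** the only adjustment mentioned is a sensitivity analysis for baseline demographic variables that differ significantly between groups. The baseline value of the outcome is not among them.
- **Table 2:** the 10M walk and 90-second balance test are scheduled at -T1 and at T4 (week 16). Both are also listed under "Eligibility screening", without cut-offs. The Objectives section describes the population as "community-dwelling older adults at risk for fall".
- **Run-in and Allocation (T0):** "participants are randomly allocated (1:2) to either a group that is the attention control", with 20 in control and 40 in cognitive training (CT).

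**The concern.** The most natural reading is a pooled-variance t-test on change scores. Subtracting baseline fixes its coefficient at 1, whereas ANCOVA estimates it. When the true slope is well below 1, the change score carries baseline noise that a covariate would remove. With only 60 participants, this is avoidable imprecision on the named fall-risk measures, and the data needed to avoid it are already scheduled.

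A second, smaller point follows from the 1:2 allocation. If CT alters the spread of responses as well as their mean, a pooled-variance test in unequal groups does not hold its 5% level. The documents do not show that this will happen.

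**Working it through.** **Inputs from the documents.** n = 20 and 40; significance at p < 0.05, taken as two-sided because sidedness is not stated; Student's t-test; week 16. There is no power or sample-size calculation to reproduce.

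**Assumptions.** Correlation r between baseline and week 16 from 0.3 to 0.9; treatment effect 0.5 SD of the measure at one visit; normal data; complete follow-up.

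**Formulas** (equal SD at both visits, set to 1):

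- variance of change = 2(1 − r)
- ANCOVA residual variance = 1 − r²
- ratio, ANCOVA to change score = (1 + r)/2, which is 0.75 at r = 0.5, 0.85 at 0.7 and 0.95 at 0.9

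**Worked case, r = 0.5.** √(1/20 + 1/40) = 0.274.

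- Change score: SD = √(2 × 0.5) = 1, noncentrality 0.5/0.274 = 1.83, power 43.5% on 58 df.
- ANCOVA: SD = √0.75 = 0.866, variance inflated by 1 + 1/56 for estimating the slope, noncentrality 0.5/(0.866 × 0.274 × 1.009) = 2.09, power 53.8% on 57 df.

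**Simulation, equal spread** (100,000 replicates; baseline x standard normal, y = r·x + 0.5·arm + e, SD(e) = √(1 − r²)):

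| r | Planned t | Ordinary ANCOVA | HC3 ANCOVA | Total N for planned test to match HC3 | 95% CI half-width, planned / HC3 (SD) |
|---|---|---|---|---|---|
| 0.3 | 32.8% | 46.1% | 44.0% | 84 | 0.65 / 0.54 |
| 0.5 | 43.4% | 53.9% | 51.6% | 74 | 0.55 / 0.49 |
| 0.7 | 63.6% | 70.1% | 68.0% | 66 | 0.42 / 0.40 |
| 0.8 | 81.2% | 84.3% | 82.7% | 63 | 0.35 / 0.34 |
| 0.9 | 98.0% | 98.3% | 97.9% | 60 | 0.24 / 0.25 |

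Noncentral-t power for the planned test is 32.9/43.5/64.0/81.0/98.0%, in agreement.

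**Restricted baseline.** Suppose screening keeps only the lower half of a normal baseline, which leaves 0.363 of its variance. Here r is the correlation *before* screening; r = 0.5 and 0.7 become 0.33 and 0.51 among those enrolled.

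| r before screening | Planned t | HC3 ANCOVA | Difference (points) |
|---|---|---|---|
| 0.3 | 40.6% | 44.1% | +3.5 |
| 0.5 | 49.8% | 51.5% | +1.7 |
| 0.7 | 68.0% | 67.7% | −0.3 |
| 0.8 | 83.2% | 82.5% | −0.7 |
| 0.9 | 98.4% | 98.0% | −0.4 |

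**Level when spread differs** (no effect, r = 0.7, control:CT residual SD ratio):

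| Ratio | Pooled t | Welch | Ordinary ANCOVA | HC3 ANCOVA |
|---|---|---|---|---|
| 0.5 | 2.3% | 5.0% | 1.8% | 4.3% |
| 1 | 5.0% | 4.9% | 4.9% | 4.5% |
| 1.5 | 8.0% | 5.0% | 8.3% | 4.8% |
| 2 | 10.5% | 5.0% | 10.9% | 5.0% |

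With strongly skewed (exponential) residuals and control SD 1.5 or 2 times larger, HC3 gives about 6.0–6.1% or 6.9–7.0%, and Welch 5.8–6.0% or 6.4–6.7%. HC3 therefore has no level advantage over Welch; what it offers is precision.

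**The case against.** The planned test is valid, the endpoint is secondary, and the trial is exploratory with no stated power target. On that view this is a preference between two sound methods. It is true that nothing in the plan is wrong here, and the point should carry no more weight than a suggestion.

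The strongest objection concerns size. The documents point towards a restricted baseline, since both tests appear under eligibility screening in a population at risk for fall. In that case the HC3 gain is under 4 points at r = 0.3 and turns into a loss of less than 1 point from 0.7 upward. A correlation of about 0.5 seen among enrolled participants must not be read against the unrestricted table, because it may correspond to 0.7 before screening. This stands, and it limits the claim. Part of the loss is the price of HC3: ordinary ANCOVA under the same restriction still gains about 2 points at r = 0.7.

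Three further objections carry less weight.

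- The exploratory mixed models might recover the precision, but the plan does not say how baseline enters them, and they are not the named comparison.
- If the t-test is meant for raw week-16 values, baseline is still left out. The variance ratio is then 1 − r², so the gain grows with correlation and the high-correlation exception disappears. The recommendation is the same.
- Dropout does not remove the gain. With the effect set so that the planned test has 80% power at full follow-up, 20% dropout gives 70.4% for the planned test against 81.2% and 76.3% for ordinary ANCOVA at r = 0.5 and 0.7 (unrestricted baseline).

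**Conclusion.** The concern holds as an efficiency point on a secondary endpoint. The omission itself is certain; the size of the benefit is not, because it depends on a correlation and a degree of baseline restriction that the documents do not give.

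Under the stated assumptions, HC3-adjusted analysis gains about 8 points of power at r = 0.5 (51.6 − 43.4), 4 at 0.7 (68.0 − 63.6), 1 to 2 at 0.8 (82.7 − 81.2), and none at 0.9. With baseline cut at its median it gains nothing from 0.7 upward. The level problem of the pooled test is conditional on unequal spread and is a secondary reason to change. The result does not affect the validity of the trial.

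**What to change.** Add to the Analysis section:

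> For each of 10M walking speed and Balance score separately, the main week-16 analysis is an ANCOVA of the week-16 value on arm and the baseline value of the same measure, with HC3 standard errors and a t reference distribution on n − 3 degrees of freedom, reported as the arm difference with 95% CI.

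Use Welch's test for any t-test that remains. If the change-score comparison is kept, naming Welch's test alone settles the level point. The same adjustment can serve other secondary endpoints that have baseline and week-16 values and suit a linear model. While editing, reconcile the conjunction between the two fall-risk components, which differs between Outcomes and Analysis.

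**Cost.** SAP wording and minor programming; no new visits or data. ANCOVA uses one degree of freedom. At equal spread HC3 gives up 2.3/2.1/1.6 power points against ordinary ANCOVA at r = 0.5/0.7/0.8. Welch in place of the pooled test costs under 1 point (42.9 v 43.4%, 62.9 v 63.6%, 80.5 v 81.2%).

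### Student's pooled-variance t-test is named for walking speed and balance at a planned 20 v 40 split, where it loses its protection if the arms' SDs differ; Welch's test costs almost nothing

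*Combined protocol and SAP*

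**What the plan says.** All references are to the combined protocol and SAP.

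- **Test for fall risk (ANALYSIS).** The secondary outcome is reduced fall risk, judged by "an increase in the 10M walking speed from baseline and an increase in the Balance test score from baseline". The next sentence is "Between group differences will be assessed using Student's t-test".
- **Other secondary endpoints (ANALYSIS).** For CANTAB, disability, gait, turning and sway: "Outcomes will be compared between groups using either t-tests or Mann-Whitney U tests as appropriate". The variance form of the t-test is not given.
- **Allocation (Run-in and Allocation (T0)).** After the run-in, "participants are randomly allocated (1:2) to either a group that is the attention control", with n=20, or the CT group, with n=40.
- **Significance (ANALYSIS).** "A value of $p<0.05$ will be considered statistically significant". Sidedness is not stated.
- **Other modelling of fall risk (ANALYSIS).** "In exploratory analyses, we will examine the change in risk of fall over time using linear mixed models for longitudinal data". No option for different variances by arm is mentioned.

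The plan nowhere mentions Welch's test, an unequal-variance option, a variance check or a robust standard error.

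**The concern.** Student's two-sample test estimates one common variance, weighting each arm's variance by its degrees of freedom. With equal arms this does little harm even when the SDs differ, because the pooled standard error still comes out right. With 20 v 40 the larger arm supplies about two thirds of the weight (39 of 58 degrees of freedom), while the smaller arm contributes more per unit of variance to the true standard error. If the CT arm is the more variable, the standard error is too large and the test loses power. If the control arm is the more variable, it is too small and the test rejects too often.

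The documents give some reason to expect the first case. CT difficulty and goals are tailored to each person (Intervention), while controls watch preselected videos (Attention Control). A response that varies between people would widen the CT arm's change scores. What is at stake is mainly power for the two fall-risk measures, in a trial of 60 people.

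**Working it through.** **Inputs from the plan.** Control n = 20, CT n = 40, nominal alpha 0.05. The plan gives no SD, effect size, power or sample-size derivation, so it has no figure of its own to reproduce other than the 5% level.

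**Assumptions.** Two-sided testing, normally distributed change scores, and SD ratios of 1.25 and 1.5 in each direction. The ratios are illustrative and do not come from the documents.

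**Step 1: bias in the pooled standard error.** With s1 the control SD and s2 the CT SD:

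- Pooled SE = √{[(19·s1² + 39·s2²)/58] × (1/20 + 1/40)}
- True SE = √(s1²/20 + s2²/40)

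*CT SD 1.5 times control (s1 = 1, s2 = 1.5).*
- Pooled: (19 + 87.75)/58 = 1.8405; × 0.075 = 0.1380; square root 0.3715.
- True: 0.05 + 0.05625 = 0.10625; square root 0.3260.
- Ratio 1.14: the pooled SE is 14% too large.

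*Control SD 1.5 times CT (s1 = 1.5, s2 = 1).*
- Pooled: (42.75 + 39)/58 = 1.4095; × 0.075 = 0.1057; square root 0.3251.
- True: 0.1125 + 0.025 = 0.1375; square root 0.3708.
- Ratio 0.88: the pooled SE is 12% too small.

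At a ratio of 1.25 the same formulae give 1.08 (CT wider) and 0.93 (control wider).

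**Step 2: type I error at nominal 5%, 20 v 40, equal means** (simulation, 200,000 trials per case; repeat runs agree to within about 0.2 points).

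| SDs | Pooled SE / true SE | Student | Welch |
|---|---|---|---|
| Equal | 1.00 | 4.9% | 5.0% |
| CT 1.25× control | 1.08 | 3.5% | 5.0% |
| CT 1.5× control | 1.14 | 2.6–2.7% | 5.0% |
| Control 1.25× CT | 0.93 | 6.7–6.8% | 5.0% |
| Control 1.5× CT | 0.88 | 8.5% | 5.1% |

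At 30 v 30 with the same SD ratios Student's test stays between 4.9% and 5.1%, so the sensitivity comes from the unequal split. With an assumed 20% dropout in each arm (16 v 32) the results barely change: 3.6% and 2.7% with CT wider, 6.8% and 8.5% with control wider.

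**Step 3: power when the CT arm is wider.** An effect of 0.8 SD needs a definition once the SDs differ. Here it is 0.8 times the root-mean-square of the two SDs, √[(s1² + s2²)/2].

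- Ratio 1.25: root-mean-square 1.132 control SDs, effect 0.906. Power about 81% Student, 84% Welch.
- Ratio 1.5: root-mean-square 1.275, effect 1.020. Power about 80% Student, 87% Welch.

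If the effect is instead 0.8 control-arm SDs, power is lower and the gap wider: about 70% v 75% at 1.25, and 57% v 67% at 1.5.

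**Step 4: price of Welch's test when the SDs are equal.** At a 0.5 SD effect, 43.6% Student v 42.9% Welch. At 0.8 SD, 81.8% v 81.1%. The loss is 0.7 points in each case.

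**The case against.** The strongest reply is that nothing in the documents shows the variances to be unequal. With equal SDs and normal data Student's test is exact. If the training did nothing to anyone, randomisation would give both arms the same distribution and pooling would do no harm. At mild ratios the distortion is small: at 1.1, about 4.3% with CT wider and 5.7% with control wider. The plan also reports SDs, so a marked imbalance would be seen. And Student's may be meant only as a generic name for a two-sample t-test.

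Much of this stands, and it limits the point to a conditional one. It does not defend the choice of test. Seeing unequal SDs in the results does not change the test named in advance, and switching afterwards adds discretion. If the name was meant generically, stating the variance form removes the doubt.

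A reader might infer more than the documents support:

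- **That false positives are the likely result.** This needs the video-watching control arm to be the more variable, and the documents suggest no reason for that. The mechanism they do suggest points to a conservative test.
- **That a pooled test is prescribed for every secondary endpoint.** Student's is named only for walking speed and balance. For the rest, the variance form is simply unspecified.
- **That planned confidence intervals or adjusted models are wrong.** The ANALYSIS section plans no confidence intervals and no baseline-adjusted comparison for these measures.
- **That the primary result is affected.** Falls are compared by Mann-Whitney U test, which does not use a pooled variance, and nothing here calls for changing it.

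**Conclusion.** The point holds as a cheap improvement to secondary analyses. Under a planned 1:2 split the plan names a test whose error rate depends on equal variances, and gives no evidence that they are equal. In the more plausible direction, CT more variable, the consequence is lost power: about 3 points at an SD ratio of 1.25 and 7 points at 1.5, with the effect measured in root-mean-square SDs. In the other direction type I error rises to about 7% and 8.5%. These sizes rest on assumed SD ratios, normal data and two-sided testing. The formulae and simulated error rates are secure, but whether this trial's SDs will differ cannot be known from the documents. The stakes are modest, since the trial is described as exploring effectiveness and the measures are secondary.

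**What to change.** In the ANALYSIS section, replace Student's t-test with Welch's unequal-variance t-test for change in 10M walking speed and balance score. In the sentence on the other secondary endpoints, state that any t-test will be Welch's. Make the change before outcome data are seen by arm, with no preliminary test of variances to choose between the two forms.

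The cost is two small wording changes and under 1 point of power if the variances are equal. No extra participants, visits or data are needed.

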Falls and Injurious Falls	Self-Report (Prospective Fall Calendar)
SECONDARY OUTCOMES	
Fall Risk	10M Walk Test 90 Second Balance Test
Cognition Speed of Processing & Response Time Attention Working Memory Task Shifting Planning and Decision Making	CANTAB Simple Response Time Rapid Visual Information Processing Verbal Recognition Memory Spatial Working Memory Intra-Extra Dimensional Set Shift

	Cambridge Gambling Task One Touch Stockings of Cambridge Stop Signal Test
Quantitative Gait and Turning Measures Gait speed (m/s) cadence (steps/min) stride length (m) turn duration (s) turn peak velocity (m/s)	APDM Inertial Sensors Walking trials under testing conditions of: Usual Pace 4-Meter walking laps x 4 Usual Pace 7-Meter walking laps x 2 (if space allows) Fast Pace 4 or 7-Meter walking laps x 2 (space dependent)
Postural Balance Measures: (medial heel-to-medial heel distance = 10 cm) ISway JERK (m^2/s^5) ISway PATH (m^2/s^2) ISway Mean velocity (MV; m/s) ISway Root mean squared (RMS; m/s^2)	APDM Inertial Sensors (ISway): (Inertial sensor at 5 th lumbar level) Static Standing 30-second trials under six conditions: normal base-firm, eye open and eyes closed; narrow base-firm, eye open and eyes closed; normal base, foam surface, eye open and eyes closed
Disability	Gill Disability Scale

Study Design

The design is a two-group randomized controlled trial following a 1-week run-in procedure comparing 16-weeks of a web-based CT intervention to attention control (See Table 2).

Baseline Visit (-T1)

If eligible for inclusion after the in-person screening, the research staff member discusses the project in detail with the individual to ascertain interest in further participation and to allow for provision of informed consent. Following informed consent, the baseline visit commences. At this visit, participants are asked about a) demographics (age, gender, race/ethnicity, formal education, income level, insurance status); b) pre-existing conditions (Charlson method); c) current medications (brown bag method). Questionnaires are administered to participants at baseline to assess: 1) social support (MOS Social Support Survey) and 2) functional status (Gill Disability Scale). Participants undergo an assessment of cognitive abilities using the Cambridge

Table 2. Study Protocol (*denotes data are collected, but is secondary outcome)

	Study period							
		Enrollment	Allocation	Post-allocation				Exit

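### Does the visit schedule leave the planned cognition (CANTAB) analyses without any post-treatment data?

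*Combined protocol and SAP*

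**What the plan says.** The text treats cognition as a repeated outcome. The Outcomes section lists CANTAB among the secondary endpoints and says: "We will explore if there is retention of benefit of the intervention on fall risk, gait, balance and cognitive outcomes one month following end" (that is, at week 20). The ANALYSIS section repeats the endpoint ("As secondary endpoints, we will measure cognitive outcomes (CANTAB"), fixes the main visit ("The primary time point of interest in this analysis is the 16-week post-randomization outcome assessment") and gives the test ("Outcomes will be compared between groups using either t-tests or Mann-Whitney U tests as appropriate"). It adds exploratory linear mixed models for change over time. It also promises descriptive summaries at baseline, mid-intervention and week 20.

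The section on the 8-, 16- and 20-week assessments says that a blinded team member "conducts participant outcome assessments at the 8-, 16- and 20-week time periods (see Table 2"). It does not list the tests done at each visit.

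Table 2 marks Cognition and CANTAB once, in the T0 column. The Baseline Visit (-T1) section puts the same test one visit earlier: "Participants undergo an assessment of cognitive abilities using the Cambridge" battery.

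**The concern.** The follow-up section points to Table 2 for detail, so the table is the natural place to learn which tests are done at which visit. If staff followed its CANTAB row as it stands, there would be no cognition score after allocation. The week-16 comparison, the mixed model and the week-20 retention question would then have nothing to analyse.

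That would be a real loss. The training targets cognitive abilities chosen for their link to falls, and CANTAB is the only cognitive outcome measure described for both arms. The training program's own testing is described only for the intervention arm.

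The baseline timing raises a second worry. The table puts CANTAB, postural sway and Gill disability at T0, the column that also holds allocation, while the text puts them at -T1. A baseline taken at T0 might seem open to measurement after the envelope is opened.

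**Working it through.** The plan gives no figure to reproduce. The check sets the Table 2 rows against its column headings and then against the text.

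**Marks by row (Table 2, outcome rows)**

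| Row | Baseline mark | Wk 8 (T2) | Wk 16 (T4) | Wk 20 (T5) |
|---|---|---|---|---|
| Fall Risk (domain) | none | – | – | – |
| 10M walk; 90 sec balance | -T1 | X | X | X |
| Cognition (domain) | T0 | – | – | – |
| CANTAB | T0 | – | – | – |
| Gait/Turning (domain) | none | X | X | X |
| APDM (gait) | -T1 | X | X | X |
| Postural Sway; its APDM row | T0 | X | X | X |
| Disability; Gill Disability | T0 | X | X | X |

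**Literal count.** Table 1 lists 8 CANTAB tests. With 0 post-baseline visits instead of 3, the literal reading removes 8 × 3 = 24 test occasions per participant.

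**Is the CANTAB row reliable?**

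1. The next row reads "Gait/Turning X X X": weeks 8, 16 and 20, with no baseline. Those are exactly the marks CANTAB lacks. The APDM gait row beneath already has its own four, so Gait/Turning does not need them. Moving those three marks up one row gives CANTAB the pattern T0, T2, T4, T5, identical to the sway and disability rows.
2. Domain rows follow no single rule. Fall Risk is empty, Gait/Turning differs from its instrument row, and Postural Sway and Disability match theirs. A Cognition row marked only at T0 is therefore weak evidence of intent.
3. A blank cell does not mean that a procedure is omitted. Vision screen and Medication review have no marks, yet the Run-in and Allocation section includes both. Exit Interview has no mark, yet the text places it after the week-20 assessment. The 90-second balance line under screening is also empty.

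**What does the text require?** A comparison at week 16 needs a week-16 score. The "retention of benefit of the intervention on fall risk, gait, balance and cognitive outcomes one month following end of the intervention" needs a week-20 score. A model of change over time needs repeated scores. The planned summaries cover baseline, week 8 and week 20 besides week 16. None of these is possible with a single T0 measurement, so the text is consistent only with follow-up testing.

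**Baseline at T0 or -T1?** The plan's own heading ties T0 to the run-in as well as to allocation, and Table 2 marks the run-in under both -T1 and T0. The envelope stays sealed until the run-in is complete. Medications and social support show the same shift (-T1 in the text, T0 in the table), which points to loose column placement. The training marks begin only in the T1 column, so even a late T0 measurement would precede training.

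**The case for a change.** The best counter-argument is that the text does not repair the table. No sentence places CANTAB at a named follow-up visit, and the follow-up section sends the reader back to Table 2. The exit interview is blank in the table but its timing is stated in words; CANTAB has no such backup. Its row is also not blank: it has a mark at T0, and the Cognition row agrees with it. Moving the Gait/Turning marks up would still leave Cognition at T0 only, and Gait/Turning may simply lack a baseline mark of its own.

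Part of this stands. The table and the text do disagree as they read, and the slipped-row explanation is an inference that only the layout of the original table can confirm. But the alternative is that the authors planned a between-group comparison, a longitudinal model and a retention question on an outcome they meant to measure once, before treatment. That is much less plausible than a misplaced set of marks. A parenthetical reference to Table 2 does not give one damaged row precedence over both the Outcomes and ANALYSIS sections.

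The claim that a null falls result could not be interpreted without cognition goes too far. Falls come from the monthly calendars and are compared by a Mann-Whitney U test that does not use CANTAB, and no mediation analysis is planned. Missing cognition data would weaken the explanation of a null result, not the result itself.

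**Conclusion.** No change to the plan follows. The literal reading (0 of 3 follow-up assessments for all 8 CANTAB tests) comes from one row of a table that is visibly irregular at that point, and it contradicts every statement in the text about the cognitive endpoint. The T0 versus -T1 difference is mainly one of labelling, because the envelope stays sealed until the run-in ends.

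This rests on two assumptions: that the three marks on the Gait/Turning row belong to CANTAB or were otherwise misplaced, and that staff carried out the follow-up testing the text implies. A look at the original table layout would settle the first. If the slip proves to be in the source table, aligning it with the text is an editorial correction. It adds no visit, test or analysis, and it has no effect on the primary falls comparison.
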